## 1.4 CLINICAL EXPERIENCE

This is the first clinical study conducted with WVE-120101. For the most up-to-date clinical experience information refer to the Investigator's Brochure (IB).

## 2 RATIONALE FOR THE STUDY

Huntington's disease is an invariably fatal disorder with no known cure. The accumulation of mHTT produced in patients with an abnormal *Huntingtin* allele leads to a progressive loss of neurons in the brain. Therefore, several therapeutic approaches for HD have focused on reduced production or removal of mHTT. However, at the present time, there are no clinical research studies in HD evaluating investigational agents that specifically target mHTT. Instead, some studies target both mutant and wtHTT, with the intent of reducing both forms of the protein to levels that will hopefully improve symptoms without leading to the deleterious effects that may

result from a reduction in wtHTT. Alternate splicing has been proposed as a mechanism for the generation of mHTT; however, ASOs should suppress this as they act on pre-mRNA.

WVE-120101 is intended to selectively target mHTT, leaving wtHTT relatively unaffected, by targeting the SNP1 variant associated with the pathogenic CAG expansion ( $\geq 36$  repeats). This should result in selective reduction of the level of mHTT protein.

## 2.1 RATIONALE FOR THE DOSES AND THE DOSING REGIMEN

The target for WVE-120101 is the mutant HTT (mHTT) mRNA, acting at the U variant of SNP1. Since no appropriate animal models that recapitulated the mutation observed in this subpopulation of HD patients were available to the Sponsor before initiation of the human studies, the proposed therapeutic dose range of 2 to 32 mg is based on the totality of the in vitro pharmacology data, which defined the concentration range needed to achieve mHTT depletion; the in vivo toxicology studies, which defined the tolerable dose range; and the clinical safety data available. The clinical starting dose was selected in consideration of the data from both single- and 13-week repeat-dose toxicology studies. Escalation to subsequent doses (approximately 4, 8, 16, and 32 mg) will be based on safety assessments from prior cohorts.

In vitro pharmacology studies demonstrated selective knockdown of mHTT mRNA and protein through preferential cleavage of the mutant allele compared with the wild-type allele. In a study conducted in patient fibroblasts that were heterozygous (U/C) for SNP1, treatment with 5  $\mu$ M (33  $\mu$ g/mL) WVE-120101 resulted in mRNA knockdown and protein reduction for mHTT but no meaningful mRNA change or protein reduction for wtHTT. The range of theoretical peak CSF concentrations in patients over the proposed dose range of 2 to 32 mg corresponds to 14 to 230  $\mu$ g/mL. Based on the concentration found to have activity in fibroblasts, the CSF concentrations that correspond to the proposed clinical dose range are expected to adequately yield knockdown of mHTT mRNA and protein.

In the single- and repeat-dose toxicity studies of WVE-120101, dose-related observations on limb dysfunction were observed in both rats and monkeys. Additional neurologic findings related to limb dysfunction were also observed in the rat which were likely related to high local concentration of test-article within a small CNS space as compared to the monkey. Furthermore, the technical complexities of IT administration to small animal models may contribute to the findings in the rat. In monkeys no findings of limb dysfunction were reported at the lowest dose (2 mg) evaluated in either the single-dose or repeat-dose studies. Application of a 10-fold safety margin to the human equivalent dose (HED), based on CSF volume, at the 2-mg dose in monkeys suggests a clinical starting dose of 2 mg. The clinical starting dose of 2 mg is also 1/13 the HED of the 0.05-mg dose in rats. Findings at this dose in rats were limited to transient, minimal clinical observations of ataxia (2 males and 3 females) after the first dose only. In addition, the dose concentration of 0.2 mg/mL that will be administered to humans is 1/10 the dose concentration administered to rats at the 0.05-mg dose (HED 28 mg) and monkeys at the 2-mg dose (HED 22.4 mg) in the repeat-dose toxicity studies.

The proposed high dose of 32 mg is expected to produce CSF exposures that are within the range of those tested and found to be well-tolerated in animals. In the 13-week monkey study, estimated peak CSF concentration at the 6 mg NOAEL dose (HED 67.2 mg) was approximately 0.48 mg/mL (based on an estimated CSF volume of 12.5 mL). In the rat, the NOAEL dose of

0.25 mg (HED 140 mg) produced an estimated peak CSF concentration of 1 mg/mL (based on an estimated CSF volume of 0.25 mL). The 32 mg dose is expected to produce a peak CSF concentration of 0.23 mg/mL, which is approximately 2-fold and 4-fold lower than those achieved in the monkey and rat, respectively, at the NOAEL-dose levels. To date, data from this study indicate that the drug has been well tolerated in patients at all dose levels evaluated. Doses of 4 mg (HED 44.8 mg) were also well-tolerated in monkeys when administered by once monthly intrathecal injection for 9 months (10 doses).

The study design is based on the need to assess the safety and tolerability of WVE-120101 by gradual exposure of a small number of patients with early manifest HD to low single doses of the study drug. If a single dose in a cohort is shown to be safe and well tolerated, that dose level will proceed to multiple dosing, and a higher dose will be administered to a subsequent cohort.

The use of a placebo in the control group is appropriate because there are currently no disease-modifying treatments for HD. The placebo group will provide a robust reference for safety and tolerability of the study drug. In particular, the placebo will help determine whether adverse events noted are related to WVE-120101 itself or to the study procedures (lumbar puncture and IT injection).

After the first dose of WVE-120101 on Day 1, the 32 mg cohort will have a 4-week follow-up period instead of an 8-week washout period. The amount of time between the first dose and the second dose was reduced because current clinical data suggest that most TEAEs occur within the first 28 days after the first dose.

Follow-up will continue for 14 weeks after the last dose, i.e., to Week 30 for participants in the 2, 4, 8, and 16 mg cohorts and to Week 26 for patients in the 32 mg cohort. The 8-week washout period was selected based on the distribution of WVE-120101 in the repeat dose (13-week) monkey study. At the end of the 8-week recovery period in the repeat-dose study in monkeys, mean WVE-120101 levels in the brain and CSF decreased to below the limit of quantitation in the brain tissue, spinal cord, and CSF in the 4- and 6-mg groups, with the exception of a few spinal cord sections that had detectable drug (0.11 µg/gm at the 4 mg dose and 0.03 µg/gm at the 6 mg dose). The concentration of WVE-120101 at 14 weeks postdose would be anticipated to be less than the lower limit of quantification (LLOQ) in all matrices (brain tissue [LLOQ 0.162µg/gm], spinal cord [LLOQ 0.162µg/gm], and CSF [LLOQ 5 ng/mL])

Patients have the option to leave the study and be treated per standard care at any time.

### **3 STUDY OBJECTIVES AND ENDPOINTS**

#### **3.1 STUDY OBJECTIVES**

##### **Primary Objective**

The primary objective of this study is to evaluate the safety and tolerability of WVE-120101 in patients with early manifest HD.

##### **Secondary objectives**

Secondary objectives of this study include:

- Characterize the pharmacokinetics (PK) of WVE-120101 in plasma.
- Characterize the exposure of WVE-120101 in CSF.
- Assess the pharmacodynamic (PD) effect of WVE-120101 on levels of mHTT in CSF.
- Assess the effect of WVE-120101 on signs and symptoms of HD, as measured by the Total Functional Capacity (TFC), administered as part of the Unified Huntington's Disease Rating Scale (UHDRS).

### **Exploratory Objectives:**

Exploratory objectives of this study include:

- Assess the effect of WVE-120101 on signs and symptoms of HD, as measured by the motor, cognitive, independence, and functional assessments, administered as part of the UHDRS.
- Assess the effect of WVE-120101 on signs and symptoms of HD, as measured by the Short Problem Behaviors Assessment (PBA-s).
- Characterize changes in magnetic resonance imaging (MRI) of the brain in patients receiving WVE-120101.

## **3.2 STUDY ENDPOINTS**

### **Primary Endpoint**

The primary endpoint is the safety and tolerability of WVE-120101, as compared with placebo, as assessed by the number of patients with adverse events (AEs), severity of AEs, number of patients with serious AEs (SAEs), and the number of patients who withdraw due to AEs.

### **Secondary Endpoint(s)**

Secondary endpoints include:

#### **Pharmacokinetics**

- Pharmacokinetic parameters of WVE-120101 in plasma at predefined time points.
- Exposure of WVE-120101 in CSF at predefined time points.

#### **Pharmacodynamics**

- Concentration of mHTT protein in CSF predose (baseline value) and at the last measured time point.

#### **Clinical Effects**

- Change from baseline (baseline value to the last measured time point) and difference from placebo in the TFC, administered as part of the UHDRS.

## **Exploratory Endpoints**

- Change from baseline (baseline value to the last measured time point) and difference from placebo in the motor, cognitive, independence, and functional assessments administered as part of the UHDRS.
- Change from baseline (baseline value to the last measured time point) and difference from placebo in the PBA-s.
- Changes from baseline MRI of the brain (Screening to last measured time point ).

## **4 STUDY DESIGN**

### **4.1 STUDY DESIGN OVERVIEW**

This is a Phase 1b/2a multicenter, randomized, double-blind, placebo-controlled study to evaluate the safety, tolerability, PK, and PD of IT WVE-120101 in adult patients with early manifest HD who carry a targeted single nucleotide polymorphism, SNP1.

This study will evaluate a single dose of WVE-120101 followed by multiple doses in eligible patients with early manifest HD. To participate in the study, patients must have documented heterozygosity for SNP1 with the thymine (T) variant on the same allele as the CAG triplet expansion. Patients who have not previously undergone SNP analysis will be required to be prescreened to determine heterozygosity for SNP1. The prescreening assessment will have a separate informed consent form (ICF).

Patients may participate in the complete study, in which they will receive all 4 doses. In order to allow for evaluation of a full multi-dose cohort (N=12), new patients may be enrolled directly in the multiple-dose portion to account for those patients who do not roll over from the single-dose portion to the multi-dose portion. These patients will receive 3 doses. Five dose cohorts will be evaluated (2, 4, 8, 16, and 32 mg).

#### **Single Dose Portion**

In each cohort, 12 patients (9 active and 3 placebo) will receive a single dose of WVE-120101 or placebo. Dosing will be initiated in a staggered manner, in which 2 sentinel patients (1 placebo and 1 active) will be dosed and observed for 48 hours in the clinic. If neither patient experiences an SAE during that period, the remaining 10 patients (2 placebo and 8 WVE-120101) will be dosed sequentially and observed in the hospital for 24 hours. Patients in the 2, 4, 8, and 16 mg dose cohorts will be assessed for safety, PK, PD, and clinical effects through the 8-week washout period after the first dose. Patients in the 32 mg cohort will be assessed for safety, PK, PD, and clinical effects through 4 weeks after the first dose.

#### **Multiple Dose Portion**

Following a safety review of the single-dose data from all the patients in a dose cohort by the Dose Escalation Committee ([Section 4.3.3](#)), the cohort will proceed to multiple dosing. Patients will receive 3 doses of WVE-120101 in the multiple dose portion, administered once every 4 weeks (for the 2, 4, 8, and 16 mg cohorts: Day 56, Day 84, and Day 112; for the 32 mg cohort: Day 28, Day 56, and Day 84). Patients in the 2, 4, 8, and 16 mg cohorts will be assessed for

safety, PK, PD, and clinical effects until Week 30 (14 weeks after the last dose). Patients in the 32 mg cohort will be assessed for safety, PK, PD, and clinical effects through Week 26 (14 weeks after the last dose).

[figure not shown]
The Dose Escalation Committee will also confirm the dose for the next single-dose cohort (Section 4.3.3). Recommendations will be reviewed by the unblinded, independent Safety Monitoring Committee (SMC) and endorsed by the chairperson.

Patients who drop out may be replaced.

Following completion of this study, all patients may be eligible to participate in an open-label extension study regardless of whether they participated in only the single dose portion, multiple dose portion, or both parts of the study.

A schematic of the overall study design and timing is provided in Figure 1.

**Figure 1 Schematic of Study Design**

Abbreviations: DEC = Dose Escalation Committee; hr = hour; SAD = single ascending dose; SD = single dose.

#### 4.1.1 Prescreening Phase

If documentation of heterozygosity and the presence of SNP1 is not available, patients must undergo Prescreening. The prescreening period is intended to identify patients who carry the targeted SNP.

Patients will sign a prescreening ICF specific to the assessments performed to determine whether they meet the eligibility criteria for heterozygosity of the targeted SNP, CAG triplet repeats ( $\geq 36$ ), and presence of the T variant of SNP1 on the same allele as the pathogenic CAG expansion ([Section 8.1](#)). This testing process is expected to take at least 6 weeks. Prescreening can happen any time before Screening. If patients meet these criteria, they will continue to the Screening Phase (Visit 2).

#### 4.1.2 Screening Phase

The screening period is intended to allow determination of patient eligibility for the study. It will begin when the study informed consent is signed. The ability of the patient to understand the consent form will be documented in the study ICF.

The Screening period will last up to 4 weeks. The required screening evaluations are outlined in the Schedule of Assessments ([Table 1](#), [Table 2](#), and [Table 3](#)). Screening assessments can occur on multiple days, provided they are within the Screening period. The Investigator will determine whether patients meet eligibility criteria and will collect the demographic and medical data permitting full characterization of the patient.

#### 4.1.3 Single-Dose Phase

Eligible patients will be randomized in a 3:1 ratio to either active or placebo treatment at the Baseline visit. Patients will receive a single IT treatment. Within 1 week prior to performing the lumbar puncture, a blood sample will be tested locally for platelet count and prothrombin time to confirm that it is safe to proceed with the lumbar puncture ([Section 8.2.6](#)). Other predose assessments may also be performed up to 1 week prior to dosing as specifically listed in [Table 1](#).

Cohorts will be dosed sequentially, following a safety review by the Dose Escalation Committee:

- 2 mg Cohort (N=12): WVE-120101 or placebo single-dose IT injection.
- 4 mg Cohort (N=12): WVE-120101 or placebo single-dose IT injection.
- 8 mg Cohort (N=12): WVE-120101 or placebo single-dose IT injection.
- 16 mg Cohort (N=12): WVE-120101 or placebo single-dose IT injection.
- 32 mg Cohort (N=12): WVE-120101 or placebo single-dose IT injection.

Dosing to all cohorts will be initiated in a staggered manner as noted in [Figure 1](#).

Two sentinel patients in each cohort (1 placebo and 1 WVE-120101) will be dosed and will then remain in the clinic for approximately 48 hours postdose. If either sentinel patient experiences an SAE during that period, the safety data will be reviewed by the SMC to determine the next steps ([Section 4.3.2](#)). If the sentinel patients do not experience an SAE during that period, the remaining 10 patients (2 placebo and 8 WVE-120101) may be dosed in a sequential fashion.

Immediately after study drug administration, all patients should be ambulatory and active for approximately 30 minutes postdose. The Investigator should note any subtle weakness or fatigue during this period. Formal physical examinations targeting the neurological system will be

performed at the time points noted in the Schedule of Assessments (Table 1). Any postdose SAEs will be monitored until resolution.

Sentinel patients will remain in the clinic and undergo assessments throughout the 48-hour postdose period. Day 3 procedures will be performed prior to discharge. Non-sentinel patients will remain in the clinic for a minimum of 24 hours postdose for assessments (Table 1). For patients in the 2, 4, 8, and 16 mg cohorts, additional assessments of safety, PK, PD, and clinical effects will be performed through the 8-week postdose washout period for all patients. For patients in the 32 mg cohort, additional assessments of safety, PK, PD, and clinical effects will be performed through 4 weeks after the first dose.

The decision regarding escalation to the next planned dose, intermediate dose, extension of the current dose level, selection of a higher dose, and if a cohort can proceed to multiple dosing will be made by an appointed Dose Escalation Committee, with endorsement from the chairperson of the SMC (Section 4.3.3). Treatment-emergent AEs that meet the Stopping Criteria will be reviewed by the unblinded SMC (Section 4.3.4). In addition, the SMC will review unblinded, aggregate safety data (Section 4.3.1).

#### 4.1.4 Multiple-Dose Phase

The Dose Escalation Committee will determine if a dose cohort can proceed to multiple dosing.

Patients who participated in the single-dose portion of the study must complete the 8-week washout period (2, 4, 8, and 16 mg cohorts) or 4-week follow-up period before receiving additional doses. Patients will visit the clinic on Day 56 (2, 4, 8, and 16 mg cohorts) or Day 28 (32 mg cohort only) for the first of 3 monthly IT doses (Days 56, 84, and 112 or Days 28, 56, and 84) (Table 1 and Table 2).

Patients who are enrolled into the multiple-dose portion of the study only will undergo the Prescreening (Visit 1) and Screening (Visit 2) visits. Patients in the 2, 4, 8, and 16 mg cohorts will not participate in Visits 3 through 7, and will receive their first dose on Visit 8. Patients will return for 2 additional doses (Visit 9 and Visit 10) and for all follow-up visits (Table 3). Patients in the 32 mg cohort will not participate in Visits 3 through 6 and will receive their first dose on Visit 7. Patients will return for two additional doses (Visit 8 and Visit 9) and for all follow-up visits (Table 3).

Within 1 week prior to each lumbar puncture, a blood sample will be tested locally for platelet count and prothrombin time to confirm that it is safe to proceed with the lumbar puncture (Section 8.2.6). Other predose assessments may also be performed up to 1 week prior to dosing, as specifically listed in Table 1, Table 2, and Table 3.

Immediately after study drug administration, all patients should be ambulatory and active for approximately 30 minutes postdose. The Investigator should note any subtle weakness or fatigue during this period. Formal physical examinations targeting the neurological system, will be performed at the time points noted in the Schedule of Assessments (Table 1, Table 2, and Table 3). Any postdose SAEs will be monitored until resolution.

Following each dose, patients will remain in the clinic for a minimum of 4 hours postdose for safety monitoring. In addition, patients will be assessed for safety, PK, PD, and clinical effects.

The SMC will periodically review unblinded, aggregate safety data (Section 4.3.1).

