## **4.2 SCHEDULE OF ASSESSMENTS**

The schedule of assessments for patients participating in the single and multiple dose portions of the study is presented in [Table 1](#) (2, 4, 8, and 16 mg cohorts) and [Table 2](#) (32 mg cohort). The Schedule of Assessments for patients participating in the multiple-dose portion of the study only is presented in [Table 3](#).

**At each relevant time point, the UHDRS, PBA-s, and Columbia-Suicide Severity Rating Scale (C-SSRS) should be performed prior to other assessments.**

**Table 1 Schedule of Assessments for Patients Participating in Both the Single and Multiple Dose Portions of the Study (2, 4, 8, and 16 mg cohorts)**

Visit	Pre-Screening a	Screening b	Double-Blind Treatment (Single Dose)		Sentinel Patient Follow-up	Follow-up		Double-Blind Treatment (Multiple Dose)			Follow-up		
	1	2	3	4	5	6	7	8 c	9	10	11 or ET	12	13
Week		-4 to 0	0	0	0	2	4	8	12	16	20	28	30
Study Day (Visit Window, if applicable) Event/Assessment		Day -28 to -1	Day -6 to Day 1 (Baseline)	Day 2 (24 ± 4h postdose)	Day 3 (48 ± 4h postdose)	Day 14 (±2)	Day 28 (±3)	Day 56 (±3)	Day 84 (±3)	Day 112 (±3)	Day 140 or ET (±5)	Day 196 (±5)	Day 210 d (EOS) (±5)
Predose/Non-dosing Days													
Patient informed consent form (ICF) Signed	X	X											
Inclusion/exclusion criteria		X	X					X					
Medical history and demographics		X											
Physical examination e		X	X	X	X	X	X	X	X	X	X	X	
C-SSRS f		X	X*			X	X	X*	X*	X	X*		
UHDRS		X	X			X	X	X	X	X	X		
PBA-s		X	X			X	X	X	X	X	X		
Drug screen g		X											
Urine pregnancy test h			X*					X*	X*	X*			
Adverse event monitoring		X	X*	X q	X q	X	X	X*	X*	X*	X	X	X
Prior and concomitant medications		X	X*	X q	X q	X	X	X*	X*	X*	X	X	X
3T MRI of the brain (without contrast)		X					X				X		
Vital signs i		X	X*	X	X	X	X	X*	X*	X*	X	X	
12-lead ECG j		X					X						
Serum pregnancy test h		X											
Clinical laboratory tests k		X	X	X	X	X	X	X	X	X	X	X	
Hepatitis (HBsAg, HCV)		X											
Blood sample for Prescreening assays l	X												
Blood sample for PK m			X	X	X	X	X	X	X	X	X		
Blood sample for immunogenicity n			X				X	X	X	X	X	X	
CSF sample for safety, exposure, and PD o			X*				X	X*	X*	X*	X r	X	
Randomization			X										

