## 6 STUDY TREATMENTS

### 6.1 METHOD OF ASSIGNING PATIENTS TO STUDY DRUG

Patients who meet all of the inclusion criteria and none of exclusion criteria will be randomized into the study on Day 1 to receive either active study drug or placebo, both administered intrathecally. Patients will receive WVE-120101 (9 patients in each cohort) or placebo (3 patients in each cohort).

In order to allow for evaluation of a full multidose cohort (N=12), new patients may be enrolled directly in the multiple-dose portion to account for those patients who do not roll over from the single-dose portion to the multi-dose portion. Treatment assignment will be performed such that these treatment-naïve patients will receive the same treatment as the patient who completed the single-dose portion.

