### **10.9.1 Adverse Events**

Adverse events will be collected and recorded from the time the patient signs the ICF at the Prescreening Visit to the study completion. The verbatim AE term will be coded to the PT and SOC using terminology from the MedDRA.

A TEAE is defined as an AE that is first identified, or is identified to worsen in intensity, at a time point occurring after the first dose of study drug. The numbers and percentages of patients with any TEAE, with any TEAE assessed by the Investigator as related to study drug or to study procedures, and with any treatment-emergent SAE will be summarized by treatment group and overall. Treatment-emergent AEs will be tabulated by relationship to study drug and by severity; these summaries will be presented by SOC and PT, by treatment group and overall. In these tabulations, each patient will contribute only once (ie, the most related occurrence or the most intense occurrence) to each of the incidence rates in the descriptive analysis, regardless of the number of episodes.

All AEs and SAEs occurring during the study (pretreatment, treatment, and follow-up) will be presented by patient in data listings. By-patient listings will also be provided for deaths, SAEs, and AEs leading to study drug discontinuation.

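### Patients who enter at the multiple-dose phase are observed less closely after their first dose than Day 1 entrants, and the TEAE tables do not separate the two groups

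*Combined protocol and SAP*

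**What the plan says.** **Day 1 entrants.** Section 4.1.3 states: "Non-sentinel patients will remain in the clinic for a minimum of 24 hours postdose for assessments". Sentinel patients stay about 48 h. The notes to Tables 1 and 2 add a targeted neurological examination at 24 h after the first dose. They also put chemistry and selected haematology samples (blood count, complement, fibrinogen) at 1, 4 and 24 h. Visits on Day 14 and Day 28 follow. At 32 mg, Day 28 is the second-dose visit.

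**Treatment-naive entrants.** Under Section 4.1.4, those in the 2 to 16 mg cohorts "will not participate in Visits 3 through 7, and will receive their first dose on Visit 8". At 32 mg they skip Visits 3 to 6 and start at Visit 7. The stay is set by the general rule for this phase: "Following each dose, patients will remain in the clinic for a minimum of 4 hours postdose for safety monitoring". In the Table 3 notes, postdose examinations run from 30 minutes to 4 h, and postdose laboratory samples are at 1 and 4 h. The next column in Table 3 is the second dose.

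**Assignment.** Section 6.1 arranges that "these treatment-naïve patients will receive the same treatment as the patient who completed the single-dose portion". Under Section 5.3.3, patients who drop out before Day 28 (Day 14 at 32 mg) are replaced to meet the dose-escalation requirements. Only later dropouts may be replaced by direct entrants to the multiple-dose part.

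**Analysis.** Section 3.2 makes patient counts of AEs, compared with placebo, part of the primary endpoint. Section 10.9.1 counts patients with any TEAE, with any related TEAE, and "with any treatment-emergent SAE will be summarized by treatment group and overall". It gives no split by entry route.

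**The concern.** Two patients on the same treatment can have the same event after a first dose and differ in the chance that it is recorded, because one is examined and sampled at 24 h and seen at Day 14 and the other is not. The lighter schedule falls in a period the protocol itself treats as important: in explaining the shorter interval at 32 mg, Section 2.1 says that "current clinical data suggest that most TEAEs occur within the first 28 days after the first dose".

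This would matter less if randomisation spread the lightly observed patients evenly. It does not, because a naive entrant takes over the treatment of a patient who did not roll over. The mix within each treatment column therefore depends on who failed to roll over and was replaced. Part of any difference in TEAE percentages, or in laboratory changes, could then reflect intensity of observation and not the drug. Adjusting for follow-up time or number of doses would not remove this, because the same post-dose period is being observed with different intensity.

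**Working it through.** **The plan's own figure.** Five cohorts of 9 active and 3 placebo give 5 × (9 + 3) = 60, matching the approximately 60 in Section 5. The documents give no expected number of naive entrants and no detection rate.

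**Schedules after the first dose** (Sections 4.1.3 and 4.1.4; Tables 1 to 3):

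| | Day 1 entrant (non-sentinel) | Treatment-naive entrant |
|---|---|---|
| Minimum stay | 24 h | 4 h |
| Targeted examination | 30 min; 1, 2, 3, 4 and 24 h | 30 min; 1, 2, 3 and 4 h |
| Postdose chemistry and haematology | 1, 4 and 24 h | 1 and 4 h |
| Later contacts up to 28 days | Day 14, Day 28 | second-dose visit at 28 days |

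**Deficit.**
- Time in clinic: 24 − 4 = 20 h.
- Contacts after the dosing day, up to 28 days: three for a Day 1 entrant (24 h, Day 14, Day 28) and one for a naive entrant, so 3 − 1 = 2. The Day 2 visit is the 24 h assessment and counts once. The Day 28 visit is matched by the naive entrant's second-dose visit, so it is not an AE-contact deficit.

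**Gap to the next visit for naive entrants.**
- Nominal: 84 − 56 = 28 days (32 mg: 56 − 28 = 28).
- Shortest: (84 − 3) − (56 + 3) = 22 days.
- Longest: (84 + 3) − (56 − 3) = 34 days. The 32 mg windows give the same range.
- Table 3 lets the predose examination and laboratory tests be done up to a week before that dose, so those can come sooner. AE questioning is tied to the dosing day.

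**Share of a column made up of naive entrants.** With k naive entrants added to n Day 1 entrants, the share is k/(n + k). The values of k are assumptions.

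| k | Active, one cohort (n = 9) | Placebo, one cohort (n = 3) | Placebo, all cohorts (n = 15) |
|---|---|---|---|
| 1 | 1/10 = 10% | 1/4 = 25% | 1/16 = 6% |
| 2 | 2/11 = 18% | 2/5 = 40% | 2/17 = 12% |
| 3 | 3/12 = 25% | 3/6 = 50% | 3/18 = 17% |

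Within a cohort the shares agree only if replacements fall in the 3:1 allocation ratio, for example 3 active (3/12) and 1 placebo (1/4), both 25%. One active replacement and none on placebo gives 10% against 0%. One placebo replacement and none on active gives 0% against 25%.

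**The case against.** Four points on the other side carry weight.

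- **Other routes of capture.** Section 9 tells patients to contact the investigator at any time if symptoms develop. Section 9.1 requires a 24-hour telephone number and questioning at each visit, so the 28-day visit covers the whole interval. Events a patient notices and remembers can still be recorded. This stands, and it confines the problem mainly to transient signs and laboratory values, plus recall. Five neurological examinations and two laboratory samples also fall within the first 4 h, and Section 2.1 does not say that most TEAEs arise after that.
- **Restricted replacement.** Only later non-rollovers can lead to a naive entrant, and replacement is optional. Early dropout after the first dose does not by itself bring lightly observed patients into an arm. This also stands.
- **Pooling is not certain.** Section 10.3.1 limits the Safety population to randomly assigned patients, while Table 3 shows treatment assignment and no randomisation for naive entrants. Section 10.1 defers detail to an SAP that is not in the text, so a split there cannot be excluded. The text available specifies none.
- **Descriptive analysis.** Section 10.9 plans no formal comparisons, and by-patient listings will exist. Readers will still compare the percentages with placebo, as the primary endpoint invites.

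A reader might go further and infer that the drug will look safer than it is, because a poorly tolerated arm gains more lightly observed patients. The documents do not support a fixed direction. Non-rollover can have other causes, and a single placebo replacement changes a three-patient group more than one active replacement changes a group of nine.

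**Conclusion.** The point holds as a limited one. After the same first exposure, naive entrants have two fewer scheduled contacts and 20 h less in clinic. Their share of each arm is not balanced by randomisation, and the stated tables do not separate them. If they are counted in the Safety population, TEAE percentages and laboratory summaries can differ between arms partly because of how closely patients were observed.

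That detection is lower in naive entrants is an inference from the schedule; the documents do not show it. The effect would be mainly on transient examination and laboratory findings. If replacements fall in proportion to allocation, the expected shares are equal.

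A reader might also want to put a number of percentage points on the loss. The documents give neither the number of replacements nor a detection ratio. A ratio assumed for first-dose events also cannot be carried over to the whole-study TEAE percentage. Each patient counts once there, and a naive entrant has three doses and 210 − 56 = 154 days (32 mg: 182 − 28 = 154) in which another event may be recorded. The size therefore stays open. The change is worth making because it is cheap.

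**What to change.** - **Section 10.3.1:** state whether treatment-naive entrants belong to the Safety population. The present wording leaves this open.
- **Sections 10.9.1 and 10.9.2:** show TEAEs and laboratory changes by entry route (Day 1 or treatment-naive) within treatment group.
- **First-dose period (first to second dose):** base any comparison across arms on Day 1 entrants, with treatment-naive entrants shown separately. The interval is at least 8 weeks in the 2 to 16 mg cohorts and at least 4 weeks at 32 mg, so a comparison across dose levels also needs a common window after the first dose.

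No visit, dose or clinical rule changes, and the data are already collected. The cost is SAP wording and one extra table split. The naive-entrant columns will be small and can only be read descriptively.
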